2.1 Study Design

The proposed study is an international, multicenter, block randomized, observer-masked, comparative effectiveness clinical trial to determine which treatment, methotrexate or mycophenolate mofetil, is more effective as first-line corticosteroid-sparing treatment for patients with non-infectious intermediate, posterior and panuveitis requiring corticosteroid-sparing therapy.

Full details which specify the definition of treatment success are given in the FAST Manual of Operations.

2.2 Study Population

Eligible volunteers diagnosed with non-infectious uveitis who have given informed consent will be enrolled in this trial. Specific eligibility and exclusion criteria are given in the FAST Manual of Operations. The proposed study schedule is listed in the FAST Manual of Operations.

2.3 Specific Aims

2.3.1 Specific Aim 1

Primary Objective. The primary objective of the study is **to establish which immunosuppressive treatment, methotrexate or mycophenolate mofetil, results in a higher rate of corticosteroid-sparing treatment success, on an intent to treat basis.** Specifically, we will compare the fraction of subjects who achieve treatment success at six months (as defined in the Manual of Operations Section 2.5.1) between the two groups.

Primary Outcome. The primary outcome for Specific Aim 1 will be the difference in the proportion of patients assigned to mycophenolate mofetil vs. methotrexate who achieve treatment success (as defined in the Manual of Operations Section 2.5.1).

Patients who experience success at 6 months with the drug to which they were originally randomized (in Specific Aim 1) will continue on the same drug for an additional 6 months. This will be called Phase I (6-12 months). Patients will then be seen every 3 months (and will be examined at 9 months and at 12 months), until success at 12 months or treatment failure at any time. Patients who fail treatment before 12 months with the initial drug will be removed from the study and treated according to best medical judgment.

Secondary Objectives

- To determine whether patients exhibit a difference in time to control of inflammation within the first six months.
- To determine whether patients exhibit a difference in time to corticosteroid sparing control of inflammation within the first six months.
- To evaluate the proportion of patients achieving treatment success at 5 months and sustaining, for at least 28 days, to 6 months.
- To evaluate a difference in control of inflammation in the posterior/pan anatomic locations only, assessed at by six months.
- To evaluate a difference in control of inflammation in the interior and anterior/intermediate anatomic locations only, assessed at by six months.
- To determine whether there is a change in best spectacle-corrected visual acuity at six months.
- To determine whether patients treated exhibit a difference in health related quality of life at six months.
- To determine if there are differences in discontinuing treatment due to each of the following reasons: safety, intolerability or lack of efficacy at six months.
- To determine whether patients exhibit a difference in the proportion of patients having macular edema at 6 months
- To determine whether patients exhibit a difference in macular thickness at 6 months
- To determine whether patients exhibit a change in vitreous haze, assessed clinically by the NEI and Davis scales at 6 months
- To determine whether patients exhibit a change in vitreous haze, assessed by the photographic grading of haze by the NEI and Davis scales at 6 months.
- To determine the proportion of patients discontinuing due to intolerability at six months.
- To determine the rate of adverse events experienced at six months.
- To determine the proportion of patients discontinuing due to serious adverse events at six months.
- To determine whether patients exhibit a change in quality of life at six months.
- Tabulate the occurrence of dose reduction used in immunosuppressive treatment (see Manual of Operations Section 3.1 for dose reduction guidelines).
- To determine efficacy of treatment in Vogt-Koyanagi-Harada (VKH) patients at six months.
- To determine the proportion of patients beginning with at least 2+ inflammation in anterior chamber cells and experience at least a 2-step reduction (i.e. decreasing from 2+ to 0.5+; 3+ to 1+; 4+ to 2+).
- To determine the proportion of patients beginning with at least 2+ inflammation in vitreous haze and experience at least a 2-step reduction (i.e. decreasing from 2+ to 0.5+; 3+ to 1+; 4+ to 2+0).

- To evaluate a difference in treatment success controlling for vasculitis at baseline, assessed at six months.
- To explore the use of a dynamic process model (such as a Hidden Markov model) to assess differences in control of inflammation.
- VKH) patients at six months.
 - Proportion of patients who started with at least 1+ inflammation levels in anterior chamber cells who achieve a decrease to 0 level of inflammation in anterior chamber cells.
 - Proportion of patients who started with at least 1+ inflammation levels in vitreous haze who achieve a decrease to 0 level of inflammation in vitreous haze.

All the above analyses will be examined at the end of Phase I (6-12 months), in addition to the following:

- To determine whether patients exhibit a difference in the probability of controlling inflammation with complete discontinuation of steroids at twelve months in Phase I.

2.3.2 Specific Aim 2

Primary Objective. The primary objective of this aim is to evaluate the clinical efficacy of switching agents as rescue therapy after initial treatment failure.

Patients who experience treatment failure (as defined in the Manual of Operations) with the drug to which they were originally randomized in Specific Aim 1 will discontinue the current treatment and be administered rescue therapy with the second drug (in a masked fashion). This will be called Phase II. Treatment failure with the first drug is defined as the inability to continue taking the drug to which the patient has been randomized, either due to intolerability, safety concerns, or lack of efficacy.

Upon declaration of treatment failure, the patient will be automatically screened for Aim 2. If eligibility criteria are met, the second treatment will be administered and data will be collected for the Phase II baseline visit. Patients will then be seen every 4 weeks until 6 months or until treatment failure with the second drug. Treatment failure and success will be defined as in Aim 1. Patients who fail treatment before 6 months with the second drug will be removed from the study and treated according to best medical judgement.

Primary Outcome. The primary outcome is the fraction achieving treatment success at 6 months after starting Phase II. Treatment success is defined as in Aim 1 and described in the Manual of Operations Section 2.5.1.

Secondary Objectives. All of the secondary 6 month objectives listed for Aim 1 will be examined for Aim 2.

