4.1. Visit schedules

4.1.1. Phase I: First-line treatment

After eligibility has been evaluated and informed consent given for participation in the trial, patients will be randomized to receive oral methotrexate or mycophenolate mofetil. Patients will continue with this course of treatment unless treatment failure occurs due to safety, intolerability or lack of efficacy. If a failure is recorded within the first 6 months, the treatment assignment will be switched to the drug not initially randomized to, and the patient will follow a new visit schedule.

Patients who are treatment failures in Phase I due to safety (i.e. a serious adverse event deemed to be related to the study drug by the Medical Monitor) may or may not proceed to

Phase II depending on the Medical Monitor’s determination. In most cases of an SAE, the patient will likely not be allowed to switch to Phase II, but in some cases, such as an SAE due to intolerability, it may be deemed safe to switch to Phase II. Even if the patient does not switch to Phase II, outcome data at 6 months should be collected if the patient is willing.

Treatment success, according to the primary endpoint, will be assessed at 6 months. If treatment has been deemed successful for a patient at 6 months, they will be provided study medication for an additional 6 months and return for additional study visits as shown below. As long as the patient stays on the first randomized medication, Visit Schedule I will be followed.

Guidelines for Visit Schedule I

- Day 1 corresponds to the Baseline-I visit, which is also the first day the patient receives treatment.
- Visit windows are determined based on the date of randomization.
- The baseline eye exam and other baseline assessments may be collected at a separate visit up to 14 days before the patient is enrolled and randomized. Laboratory measurements may be collected within either 4 weeks or 90 days prior to the date of randomization, depending on the laboratory test.
- There should be a minimum of 2 weeks between each study visit.
- Data for the baseline and follow-up visits may be collected anytime within the visit window.

Table 9: Visit Schedule Phase I (0-6 months) or Phase II

Visit	Window Days/Weeks
Baseline*	
Week 2	±3 days
Month 1*	±15 days
Month 2	±15 days
Month 3	±15 days
Month 4	±15 days
Month 5	±15 days
Month 6	-15 to +30

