3.2 Analysis

3.2.1 Summary of Principal Outcome Variables and Regression Variables

Variables

- Primary outcome: Patient treatment success by six months (see MOP, Section 2.6)
- Patient treatment success at twelve months (Phase I)
- Successful control of inflammation in both eyes by twelve months, with complete discontinuation of corticosteroids
- Best spectacle-corrected visual acuity, at baseline and at the time of failure or six months (two observations per patient)
- Time to corticosteroid sparing control of inflammation (6 months and 12 months)
- Change in health related quality of life subscores (PCS and MCS) from SF-36 and Vision Related Quality of Life from NEI-VFQ-25 and IND-VFQ at six months and twelve months

- Reason for discontinuation of therapy (if applicable) at six months and twelve months
- Macular thickness at baseline, and at six months and twelve months
- Presence of macular edema at six months and twelve months
- Vitreous haze assessed clinically by the NEI and Davis scales at baseline, six months, and twelve months
- Vitreous haze as assessed by the photographic grading of haze by the NEI and Davis scales at baseline six months and twelve months
- The proportion of patients discontinuing due to serious adverse events at six months and twelve months
- Tabulate the occurrence of dose reduction used in immunosuppressive treatment.
- Treatment efficacy of VKH patients at six months and twelve months
- Treatment efficacy of patients with vasculitis at enrollment

Note that the presence of cataracts renders assessment of vitreous haze more difficult. Vitreous haze measurements in the presence of certain cataracts will be considered less reliable, and this will be considered in statistical modeling. Analyses will be repeated for differing assumptions about this bias. A maximum likelihood latent variable model will be considered, in which a true underlying vitreous haze level predicts an observed value. The observation model will include a higher probability of yielding a large observed value in the presence of a cataract.

Major independent variable of interest

- Treatment assignment (methotrexate or mycophenolate mofetil)

Additional regression variables used in selected analyses

- Anatomic location (coded dichotomously as either intermediate (code 0) or as being either posterior uveitis or panuveitis (code 1))
- Country
- Study site
- Gender
- Age
- Baseline quality of life (health and vision related)

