The primary analysis is a logistic regression with treatment arm as a predictor. For the primary analysis, we propose to use study site as a *random effect* (random intercept model). The null hypothesis is that the regression coefficient for treatment arm equals zero, which will be tested using a likelihood ratio test with one degree of freedom. We will also fit the following models: (a) a model including drug, site, and drug \times site interaction, (b) a model including only drug and site, (c) a model including only drug and country, and (d) a model with drug, country, drug-country interaction, and site within country. Countries or sites with fewer than three observations will be pooled together. Provided there is no evidence of treatment \times site interaction or treatment \times country interaction, we will report pooled treatment effects and confidence intervals. In the event evidence suggests a difference between treatment sites, we will report treatment effects by site, and repeat the analysis excluding particular sites. Similarly, evidence of a treatment \times country interaction will lead us to report treatment effects and confidence intervals by country.

Simulations suggest that use of a model containing interaction terms between site or country and treatment for the primary analysis is undesirable. Such a procedure results in modest loss of power unless the treatment effect is of opposite sign in different sites or countries.

The hypothesis test is to be two-sided with alpha of 0.05. We propose to compute the P-value by permutation testing, based on the block randomization scheme.

Prespecified Subgroup Analysis.

The prespecified subgroup analysis will test the hypothesis that there is a treatment effect separately in each anatomic group, using a logistic regression model.

We denote the two anatomic groups by X_i^3 , which equals 0 when the patient is in the intermediate group and 1 when the patient is in the posterior/pan group. In the intermediate subgroup, we plan to determine whether there is evidence of a treatment effect (regardless of the effect in the posterior/pan group). Specifically, we will conduct this analysis in two ways: anatomical site at enrollment (split into three categories: anterior, anterior/intermediate or intermediate only, and posterior/panuveitis), and anatomical location by history (split into two

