3.4 Sample Size Evaluation

3.4.1 Primary Calculation

The sample size for the trial will be 216 subjects, which we anticipate will provide approximately 80% power to detect a difference of 20% in the proportion of patients achieving control of inflammation at six months between the methotrexate and mycophenolate mofetil groups.

This sample size was determined based on the primary objective (superiority comparison of mycophenolate mofetil to methotrexate) and primary endpoint (treatment success). We assumed an effect size of 20%, as this was deemed to be clinically meaningful, and well within the distribution of the investigators' prior beliefs from published retrospective studies.

An approximate sample size is provided by the formula

$$2N = \frac{4(Z_{\alpha} + Z_{\beta})^2 \bar{p}(1-\bar{p})}{(p_c - p_i)^2} \quad (5)$$

(see Friedman et al. 2010), where α is the significance level (0.05, two sided), β is one minus the power (the desired power is 80%), p_c is in this case the probability of success in the methotrexate group (we estimate this at 0.4), p_i is the probability of success in the mycophenolate mofetil group (we estimate this at 0.6), and \bar{p} is $\frac{1}{2}(p_i+p_c)$. We assume 10% will be lost to follow-up in the first six months; details are given in the full proposal. This yields approximately 108 patients in each of the two groups, for a total of $2 \times 108 = 216$ subjects.

A power table is provided below as a sensitivity analysis (to show how the detectable effect size changes with varying success rates).

Success rate with Drug A	80% Power		90% Power	
	Detectable effect size	Success rate with Drug B	Detectable effect size	Success rate with Drug B
20%	18%	38%	21%	41%
30%	20%	50%	23%	53%
40%	20%	60%	23%	63%
50%	20%	70%	22%	72%
60%	19%	79%	21%	81%

Simulation confirms that this method yields adequate sample sizes for the logistic regression (results not shown).

Note that for the final analysis, the critical value will be adjusted slightly because of the interim analysis.

Sample size readjustment

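### Month-12 between-arm tests of macular edema, macular thickness, vitreous haze and quality of life (and acuity, if analysed) would compare arms already selected on month-6 success; these results should be descriptive

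*Combined protocol and SAP*

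**What the plan says.** **Who reaches month 12.** Protocol 4.1.1: "If treatment has been deemed successful for a patient at 6 months, they will be provided study medication for an additional 6 months". Patients who fail in months 0-6 normally switch drug and are followed for six months from failure (Protocol 1.2, Aim 2). Of those who succeed at month 6 and fail later, SAP 2.3.1 says: "Patients who fail treatment before 12 months with the initial drug will be removed from the study and treated according to best medical judgment". In the form schedule (Protocol 4.2) month 12 appears only under Phase I, and Protocol 5.1 gives the 12-month questionnaires only to patients who continue after success.

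**What is analysed there.** SAP 2.3.1 carries the whole six-month list forward: "All the above analyses will be examined at the end of Phase I (6-12 months), in addition to the following". SAP 3.2.1 includes "Macular thickness at baseline, and at six months and twelve months", and also lists macular edema, vitreous haze and quality of life at twelve months. Its Inclusion of Data rule takes all outcomes for this period from a window around the 12-month visit. SAP 3.2.2 introduces the planned secondary analyses as tests of whether treatment assignment affects the outcome.

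**What is handled differently.** SAP 3.2.2 item 1 requires control at both month 6 and month 12, and item 7 takes steroid-free control out of everyone who started therapy. Acuity is listed in SAP 3.2.1 at baseline and at failure or six months, with no twelve-month value. SAP 3.2.2 items 4 and 5 use a time-of-failure value for acuity and quality of life.

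**The concern.** Entry to months 6-12 depends on the primary outcome. If the drugs differ in success rate, the arm with fewer successes keeps a smaller group, plausibly one with a better underlying prognosis. Randomisation does not balance the two groups of successes, so a difference between them mixes drug effect with selection. An absence of difference could be read as no long-term difference between the drugs when selection has offset a real one.

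The SAP recognises the mechanism elsewhere: section 3.5 warns that unequal loss of patients who are doing well could flatter the poorer drug. That caution concerns loss planned at about 10%. At month 12 the design itself leaves out 40% of retained patients in one arm and 60% in the other, and no analysis set, caveat or descriptive label is given for these outcomes.

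**Working it through.** **Inputs.** SAP 3.4.1: success on methotrexate ("we estimate this at 0.4") and on mycophenolate ("we estimate this at 0.6"), 108 per arm, 10% loss by month 6. SAP 3.4.2: a further 5% loss between months 6 and 12; SDs of 6.5 letters, 6.72 SF-36 points and 160 microns; detectable differences of 2.63 letters, 2.57 points and 65 microns. SAP 3.2.2: "The hypothesis test is to be two-sided with alpha of 0.05".

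**1. The SAP's own 12-month power.** SAP 3.4.2 states about 78% for a 20-point difference in 12-month success. Formula: power = Φ{[Δ − 1.96√(2p̄(1−p̄)/n)] / √([p₁(1−p₁)+p₂(1−p₂)]/n)}, with Δ = 0.2 and p̄ = 0.5.
- n = 108 × 0.85 = 91.8 per arm gives 77.8%.
- n = 108 × 0.90 × 0.95 = 92.3 per arm gives 78.0%.
- With month-6 successes only (55.4 and 36.9) it would be 47%.

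So that endpoint was planned on all randomised patients less loss.

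**2. Patients with month-12 data for the other outcomes.**
- Mycophenolate: 108 × 0.90 × 0.60 = 58.3 at month 6; × 0.95 = 55.4 at month 12.
- Methotrexate: 108 × 0.90 × 0.40 = 38.9 at month 6; × 0.95 = 36.9 at month 12.

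These counts are before any failures in months 6-12, for which the SAP gives no rate.

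**3. Power at the SAP's detectable differences.** For continuous outcomes, power = Φ{d / (SD√(1/n₁+1/n₂)) − 1.96}; for edema, the two-proportion calculation.

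| Outcome | About 92 per arm | 55.4 and 36.9 |
|---|---|---|
| Acuity, 2.63 letters | 78% | 48% |
| SF-36, 2.57 points | 74% | 44% |
| Thickness, 65 microns | 79% | 48% |
| Edema, 19% and 38% | 82% | 49-52% |

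**4. Selection bias (assumed model).** Let one standard normal prognosis decide success, and let it correlate ρ, in the favourable direction, with the month-12 outcome. The mean prognosis of the top fraction p is φ(z_p)/p.
- 60% arm: 0.644 SD. 40% arm: 0.966 SD.
- Bias against the drug with more successes: (0.966 − 0.644) × ρ = 0.322ρ SD.

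The documents give no ρ, so a range is shown. Simulation with 2,000,000 draws per arm gave 0.095, 0.160 and 0.226 SD. The last column is the simulated rejection rate of a nominal 5% t-test with 55 and 37 patients and no true drug effect on the outcome (4,000 replicates; 4.6% at ρ = 0).

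| ρ | Bias, SD | Letters | SF-36 points | Microns | Rejection |
|---|---|---|---|---|---|
| 0.3 | 0.10 | 0.6 | 0.6 | 15 | 8% |
| 0.5 | 0.16 | 1.0 | 1.1 | 26 | 12% |
| 0.7 | 0.23 | 1.5 | 1.5 | 36 | 23% |

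**5. Sensitivity to why patients fail.** SAP 3.4.2 expects discontinuation for tolerability in 13% (methotrexate) and 4% (mycophenolate), and for safety in 5% of each. If these are independent of prognosis, success among the rest is 0.40/0.82 = 48.8% and 0.60/0.91 = 65.9%. The means become 0.817 and 0.556 SD, and the bias 0.261ρ SD: 0.08 at ρ = 0.3 and 0.13 at ρ = 0.5.

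**6. Shrinkage or reversal.** The detectable effects are 2.63/6.5 = 0.40, 2.57/6.72 = 0.38 and 65/160 = 0.41 SD. At ρ = 0.5 a true 0.40 SD benefit appears as 0.24, 0.20 as 0.04, and 0.10 as −0.06. Reversal needs a true effect below 0.322ρ SD.

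**The case against.** The best reply is that the SAP never says these analyses are restricted to successes. SAP 4.1 makes all randomised patients the primary efficacy population, SAP 3.5 puts intent to treat first, and the carried-forward sentence says only that the analyses will be examined. SAP 3.2.2 writes out specific 12-month models only for the success and steroid-free endpoints; its edema and thickness items specify month 6. A reader might therefore infer a deliberate, fully specified successes-only test, and the documents do not support that. What stands against the reply is that month-12 data exist only for month-6 successes, the window rule points to those data, and the secondary analyses are framed as tests of assignment.

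The time-of-failure rules are a fair point for acuity and quality of life. Carried to month 12, they would bring failures in with values from the time of failure. The SAP does not say so and its window rule points the other way, so this is an ambiguity to resolve.

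Patients who fail in months 6-12 do have failure-visit forms (eye examination and quality of life required; acuity, OCT and fundus if applicable). They too were month-6 successes, so their data do not restore the randomised comparison.

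A reader might extend the point to adverse events. The documents do not support that: the safety population is everyone who received study drug (SAP 4.1), item 13 is a tabulation with confidence intervals, and SAP 7.2.1 presents its additional testing as being for insight only. Events can be analysed from randomisation.

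**Conclusion.** The point holds for macular edema, macular thickness, vitreous haze and quality of life at month 12, and for acuity if it is analysed then. Followed as written, the SAP would test treatment arm in about 55 and 37 patients selected on the primary outcome. That selection follows from the design; the two counts rest on the SAP's planning rates.

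The direction and size of the bias are less certain. Under a single normal latent prognosis the bias is about 0.32ρ SD against the drug with more successes, or 0.26ρ SD if tolerability and safety failures are independent of prognosis. It vanishes if success rates and the make-up of the successes are the same in both arms. A reader might infer that the month-12 results must favour the less effective drug or reverse its disadvantage. The documents do not support this: they give no ρ, and effects of the size the SAP is powered for would be shrunk, with only small ones reversed.

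The six-month primary analysis and the binary 12-month success and steroid-free endpoints are not affected.

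**What to change.** Amend SAP 2.3.1 and 3.2.1 as follows.

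- State that month-12 results for edema, thickness, haze, quality of life and, if kept, acuity among month-6 successes are descriptive: estimates by arm, with no between-arm test and no drug-effect claim.
- Keep month-12 between-arm tests for the binary success and steroid-free endpoints, with all randomised patients in the denominator.
- Reconcile the carried-forward sentence in SAP 2.3.1, the variable list and window rule in SAP 3.2.1, and items 4 and 5 of SAP 3.2.2, so that it is clear whether acuity is analysed at month 12 and whether acuity and quality of life then use time-of-failure values.
- Optionally, compare starting strategies by initial assignment using the Phase II month-6 visit for switchers, labelled exploratory. It is incomplete. Patients who failed early are measured before month 12. Laboratory serious-event failures do not switch, other safety failures may not, and patients who miss the two-week entry window generally do not enter Phase II. Those who fail in months 6-12 have no matching visit.

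The cost is SAP wording and some table shells, with no new data. The sponsor gives up p-values for several 12-month secondary outcomes.
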